9. RESEARCH DESIGN AND METHODS

The treatment duration for the study will begin 0-7 days of life and continue until 40 weeks adjusted age (full-term). Intravenous treatment will start in the first few days of life and will continue until the infant can tolerate enteral nutrition. Once enteral feeds can be started, supplementation by mouth will begin until 40 weeks adjusted age.

Laboratory blood draws:

Prior to enrollment: In addition to routine tests, blood will be tested for AST and ALT. If these tests are interpreted as abnormal, the infant will not be considered for enrollment in the study as it will be deemed a contraindication to supplemental Omegaven.

While the infant is growing in the hospital, the doctors will need to check the infant's blood to make sure the infant is developing as expected.

If the infant is enrolled in the study, the infant will be randomized in blocks of 4 by gestational age to one of two groups. The control group will get standard of care nutrition, and the experimental group will get standard of care nutrition with supplemental omega-3 fatty acids. Soon after birth, most premature infants need additional nutrition through the vein (intravenous). For the control group, there will be no changes to the standard of care parenteral nutrition. For the experimental group, the infant will receive Omegaven, an intravenous lipid preparation prepared from highly refined fish oil, in addition to the standard of care parenteral nutrition. In the instance that twins are enrolled in the study, the siblings will be randomized as one to receive the same treatment per request and approval from [name].

Transition – For the second/interventional group, Omegaven will be stopped once enteral feeds are at 120 ml/kg and enteral Oil will be started. There will be no overlap of parenteral and enteral n-3 supplementation.

If the infant can start using his/her own stomach for digestion, he/she will get fatty acid supplementation. In the control group, the infant will receive standard of care feeding. If the infant is in the experimental group, the infant will get one fourth (1/4) teaspoon per kilogram per day ($1.25\text{mL/kg/day} = 400\text{ mg omega3 per kg of fish oil per day}$) of Carlson's fish oil oral solution. Dose will be divided to at least twice a day dosing for better tolerance.

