Fatty acid supplementation will continue until the baby is full term (40 adjusted weeks of age). If the infant is discharged before he/she is full-term, the infant will be sent home with a bottle of the fatty acid oral solution for the infant to continue daily until he/she is full-term (40 weeks of age). The infant's nutritional needs will be carefully monitored by his/her doctor and nutritionist per NICU protocols.

To monitor the amount of fatty acid nutrition getting into the blood, we will check the infant's blood. As much as possible, we will coordinate the study blood collection at the same time as the routine NICU blood draws. We will collect 1.3 milliliters of blood at 4 different times spread apart while the infant is in the hospital. At each time point, we will collect about 1/4 teaspoon of blood, for a total of about 1 teaspoonful.

The blood draws will occur as the following four time points:

- Blood draw T0= Prior to parenteral nutrition, within 1st 3 days of life. This blood collection should be

taken from cord blood. If cord blood is not available, sample will be collected from a UAC, UVC, or peripheral blood draw concurrent with SOC.

- Blood draw T1= 5 days after parenteral nutrition is started; grace period +/-3 days therefore total 2-8 days after parenteral nutrition started.
- Blood draw T2= 5 days after enteral nutrition full feeds have arrived; grace period +/-3 days therefore total 2-8 days after full enteral nutrition arrived.
- Blood draw T3= Prior to discharge from hospital coinciding with time that ROP may be present, ≥ 35 weeks adjusted age.

This blood will be used for looking at what new genes (mRNA) the infant is making and to check how many and what kind of fatty acids the infant has in the blood. Before testing, the blood will be stored in a storage facility at the UCSD Department of Ophthalmology Blood Bank and labelled with a barcode without the infants' personal information. This is not the infant's DNA, and no DNA will be isolated or tested. Samples will be stored for 10 years. After this time point, all samples will be destroyed if not used by that time. If the parent decides to withdraw consent the blood samples that were already drawn will be destroyed, however, any previously obtained data from sample testing will be kept.

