12. INFORMED CONSENT

Parents of potential subjects will be asked to provide written consent, using an IRB-approved consent form. The consent process will take place prior to performing any study related procedures and in a private location. The potential subject will already be admitted to the hospital. The Investigator or study coordinator will describe the study, including detailed information about risks and benefits, to the parents of potential subjects. The investigator or study coordinator will provide the parent with an IRB-approved consent form. Parents will be given ample time to read this consent form at the same visit or may take it with them to read at another time. Parents will be given the opportunity to ask and receive answers to all questions they may have about the study, its risks and benefits, or the consent form itself before signing the consent form. As this research is subject to HIPAA privacy rule provisions, participants will also be requested to sign a separate authorization for the use of protected health information (i.e., HIPAA form specific to the research study). The investigator or study coordinator will obtain informed consent in a language understood by the prospective participant or their legally authorized representative, using certified translations of study documents and qualified translators, where applicable.

For the follow-up eye exam data, we will obtain a signed medical release authorization form for any patients scheduled to receive an exam outside of UCSD as their SOC.

Subjects who fulfill the eligibility criteria will be offered further participation in this study. Only subjects who have consented and provided HIPAA authorization will have identifiers or linked information (e.g., subjects initials, study numbers, etc.) recorded on the Screening/Enrollment Log.

All signed consents will be maintained in marked binders, secured in locked filing cabinets within private administrative offices at UCSD's Clinical Teaching Facility on campus accessible to study coordinators and principal investigators only.

A copy of the HIPAA authorization and informed consent form(s) that will be used on this study are attached to this IRB application for your review.

Oral consent will be obtained from the maternal subjects for completion of the maternal questionnaires. No PHI will be collected from the mother nor will her medical records be accessed.

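### T0 and T1 are timed from parenteral nutrition, not from randomisation or study lipid, so an on-protocol T1 can precede the first Omegaven dose and T0 can be unobtainable

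*Combined protocol and SAP*

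**What the plan says.** All but one of the relevant statements are in Section 9; the consent rule is in Section 12.

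- **T0:** "Blood draw T0= Prior to parenteral nutrition, within 1st 3 days of life". Cord blood is the preferred source. The fallback is: "If cord blood is not available, sample will be collected from a UAC, UVC, or peripheral blood draw concurrent with SOC".
- **T1:** "Blood draw T1= 5 days after parenteral nutrition is started; grace period +/-3 days", which the protocol spells out as 2-8 days after nutrition starts. The Lipidomics paragraph gives a different window for the same sample, 5-8 days.
- **Parenteral nutrition:** standard care that most preterm infants need soon after birth. No start day is given, and it is not linked to enrolment.
- **Study treatment:** "The treatment duration for the study will begin 0-7 days of life". The next sentence is looser: "Intravenous treatment will start in the first few days of life". Omegaven is given to the experimental arm "in addition to the standard of care parenteral nutrition", once AST and ALT have been checked and the infant has been enrolled and randomised.
- **Consent (Section 12):** "The consent process will take place prior to performing any study related procedures and in a private location". The infant is by then an inpatient, and parents may take the form away to read.
- **Analysis (Section 9, Statistical Analysis and Power Calculations):** change from baseline DHA is modelled with group, time and their interaction, plus a random intercept and slope. The primary outcome is DHA at 40 weeks, and power is computed on the pre-post difference.

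**The concern.** The first two samples follow one clock (the start of standard nutrition) and the intervention follows another (consent, liver tests, randomisation, first dose). Nothing ties the two together. Two consequences follow.

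First, a T1 sample in the Omegaven arm can be drawn, fully on protocol, before any Omegaven has been given. Such a sample says nothing about the intervention, yet the model counts it as a treated observation. Even among dosed infants, exposure at T1 varies with the lag between nutrition and first dose.

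Second, T0 must precede nutrition, but consent must precede any study procedure and treatment may still start up to day 7. The protocol therefore admits infants whose T0 window has closed. It does not say whether cord blood may be kept before consent, or what happens when T0 is missing. T0 is the baseline of the planned change analysis, so its loss could matter at every later visit.

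**Working it through.** **1. The plan's own power figure.** Inputs from Power Calculations: 20 per arm, mean pre-post differences of 42 and 27 µmol/L (difference 15), SD 15 (the largest of six considered), two-sided 0.05.

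- Noncentrality = 15 / (15 × √(2/20)) = 3.162.
- Normal approximation: Φ(3.162 − 1.960) = 88.5%.
- Exact two-sample t, 38 df: 86.9%.

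The stated power of over 80% is reproduced.

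**2. Can T1 precede the first dose?** T1 day of life = nutrition start day + 2 to 8 (nominally + 5). The latest permitted treatment start is day 7.

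| Nutrition starts | Earliest T1 | Nominal T1 | Nominal T1 relative to a day-7 first dose |
|---|---|---|---|
| day 0 | day 2 | day 5 | 2 days before |
| day 1 | day 3 | day 6 | 1 day before |
| day 2 | day 4 | day 7 | same day |
| day 3 | day 5 | day 8 | 1 day after |

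So it can. With nutrition on day 0, the earliest permitted T1 falls 5 days before a day-7 dose. Under the 5-8 day window it is still possible with nutrition on day 0 (T1 on day 5 or 6) or day 1 (T1 on day 6).

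**3. How often?** The documents give neither the nutrition start day nor the lag from consent to dose, so this step rests on assumption: nutrition on day 0, T1 uniform on (a, b), first dose uniform on (0, m), the two independent. For a ≤ m ≤ b,

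P(T1 before dose) = (m − a)² / [2 (b − a) m], and zero if m ≤ a.

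| T1 window | Start within 7 days | Within 5 days | Within 3 days |
|---|---|---|---|
| 2-8 days | 25/84 = 29.8% | 9/60 = 15.0% | 1/36 = 2.8% |
| 5-8 days | 4/42 = 9.5% | 0% | 0% |

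The 3-day column is one reading of the looser treatment-start sentence. Nutrition on day 0 is the least favourable case. Weighting equally every whole-day pair of first dose (from nutrition start to day 7) and T1, the pre-dose share for nutrition on days 0, 1, 2 and 3 is:

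- 2-8 day window: 15/56, 10/49, 6/42 and 3/35, or 27%, 20%, 14% and 9%.
- 5-8 day window: 3/32, 1/28, 0 and 0, or 9%, 4%, 0% and 0%.

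**4. Effect on the T1 contrast.** If undosed infants show no effect and dosed infants share a common one, the expected T1 difference is multiplied by (1 − share): 0.70 at 29.8%, 0.905 at 9.5% and 0.97 at 2.8%.

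**5. Missing T0.** Only if the response is literally T − T0, so that infants without T0 drop out, does the effective sample shrink. For assumed losses (exact t, difference 15, SD 15):

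| T0 missing | Per arm | Power |
|---|---|---|
| 0% | 20 | 86.9% |
| 10% | 18 | 83.0% |
| 20% | 16 | 78.1% |
| 30% | 14 | 72.1% |

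**The case against.** The strongest reply is that Omegaven is described as part of the parenteral regimen. The Nutrition paragraph of Section 9 gives it the same initial range as control Intralipid (0.5 to 1 g/kg/day), with Intralipid covering lipid needs above 1 g/kg/day. Section 26 has nurses hang it alongside standard TPN. If the two start together, nutrition start is a sound and objective anchor in both arms. That reading is plausible, but no passage requires it. Consent, liver tests and randomisation all come before the first dose, and the day 0-7 allowance leaves room for a lag.

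Three stronger readings are tempting, and the documents support none of them.

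- **That 30% of T1 samples are untreated and power falls to 58%.** The 58% comes from shrinking 15 to 10.5 (15 × 0.70) with SD 15 and 20 per arm. Nothing is powered at T1: the difference of 15 is the plan's input for DHA at 40 weeks, and no T1 effect is stated. The 30% also pairs the wider T1 window with the later start statement and the earliest nutrition day.
- **That any infant consented after nutrition starts has no T0.** Cord blood predates nutrition. T0 is lost only when there is neither usable cord blood nor another pre-nutrition sample that may be used.
- **That a missing T0 necessarily removes the infant.** The plan wants a mixed model on all available data. If the baseline sample is one of the time levels, the infant still contributes. The plan's phrase for the response leaves this open.

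**Conclusion.** The point holds as a gap in the sampling schedule that should be closed. From the protocol's own windows, an on-protocol T1 in the Omegaven arm can precede the first dose, and an infant consented after nutrition starts without usable cord blood has no on-protocol T0.

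The frequency of either event cannot be derived from the documents. Under the stated assumptions (nutrition on day 0, uniform and independent timing) pre-dose T1 ranges from about 30% to 9.5% to 0-3%. Most of that spread comes from contradictions within Section 9: two T1 windows and two treatment-start statements. Later nutrition lowers the figures.

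The damage is a blurred group-by-time effect at T1. A pre-dose T1 does not alter the 40-week contrast, and the stated power of over 80% is not shown to be wrong. Missing T0 reduces power only under a literal change-from-baseline response; on the plan's most conservative SD, a 10% loss then still leaves 83%, and a 20% loss gives 78%.

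**What to change.** 1. Time T1 from randomisation in both arms. Using first dose in one arm and randomisation in the other would not be a common anchor whenever dosing lags. Record days since first study lipid in the Omegaven arm, so that any remaining pre-dose T1 is visible.
2. Use actual days since randomisation as time in the model.
3. Define baseline as the last sample before randomisation or first study lipid, and record whether standard nutrition had begun. Before randomisation is the cut-off that applies identically to both arms.
4. Model DHA itself, with the baseline sample as a time level, so that infants without T0 still contribute under the missing-at-random assumption the plan already makes. State this as the handling of missing T0.
5. Reconcile the 2-8 and 5-8 day T1 windows and the two statements of when treatment begins, all in Section 9. Which treatment-start statement applies is for the investigators to settle.
6. Reconcile T0 with the consent passages: state whether consent can precede delivery, and whether cord or residual clinical blood may be used once consent is given.

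The cost is protocol and analysis wording, with no extra draws. The small downside is that some baselines will follow standard lipid exposure, which is why item 3 asks for that to be recorded.

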We will examine the infant's eyes according to the standard NICU guidelines and protocols. We will also examine the infant's eyes in our eye clinic after discharge over time as we do for all premature infants to support the infant's visual development.

During the study:

Maternal diet questionnaires will be administered to the maternal subjects following enrollment. This questionnaire is the Omega 3 Fatty Acid Questionnaire and has been validated in a related study for this fatty acid¹⁹. It is anticipated to take 10-15mins to complete. Mothers will be asked to complete this questionnaire at the time of enrollment.

Blood samples will be collected 4 times. When possible, and in the majority of blood draws, 1.3 cc of whole blood will be collected at the same time as other blood draws to avoid multiple sticks. Whole blood will be collected in a green or lavender top tube. One hundred μ l of plasma will be isolated, and this will be aliquoted into in two tubes and frozen (-80°C).

Lipidomics: Plasma fatty acids will be tested using a preprandial whole-blood sample (1.3 mL) drawn 2-4 hours after the parenteral nutrition (PN) had ended for the day and after enteral feedings were held for 3 hours if the patient was also fed enterally. The schedule for sampling will be as follows: prior to parenteral nutrition within ≤ 3 days of life; within 5-8 days after parenteral nutrition is started; within 5-8 days after enteral nutrition full feeds is started; and prior to discharge from hospital coinciding with time that ROP may be present. The samples will be sent to [name] of Engineering in Medicine Laboratory at UCSD or another UCSD laboratory for internal validation of assays. [name] lab (UCSD Department of Ophthalmology) or another laboratory with similar capabilities will perform some of the RNA isolation and analysis. Capillary gas chromatography/mass spectroscopy will be the one of the main methods used to determine the phospholipid profile.

Transcriptomics: From the plasma isolated from the whole blood samples, 50 μ l will be used for mRNA isolation. This will be collected and frozen as the study is ongoing. The fold expression of genes associated with the fatty acid synthesis pathway, hypoxia and pro-angiogenic pathways will be correlated with clinical disease.

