Eye exams: All infants will get eye exams according to standard NICU protocols. Serial eye exams will be performed according to the usual intervals, which is until retinal vascularization has matured or active ROP has stabilized, usually at 1-2 months post-term. The area of vascularized retina, clock hours of neovascularization, and amount of retinal vascular dilation and tortuosity will be measured by indirect ophthalmoscopy in all infants at each clinical exam by an ophthalmologist masked to the treatment group. Stage of retinopathy of prematurity and need for ROP treatments will be measured at 40 weeks gestation plus or minus three weeks and followed over time. Infants with ROP will be monitored over time for longer term visual and anatomic outcomes. For both groups, infants will have SOC eye examinations prior to discharge around 40 weeks GA (≥ 38 wks GA). For both groups, if infant is discharged prior to 38 weeks GA, we will collect follow-up data from their outpatient follow-up eye exam from UCSD or other provider

Nutrition: Omegaven has been approved by the FDA for use in children and infants with parenteral nutrition associated liver disease (PNALD). In this study we intend to use Omegaven under an IND exemption to study the use of the drug in reducing the incidence and severity of retinopathy of prematurity (ROP). Our aim is to differentiate the phospholipid profiles and gene expression pathways of at-risk very low birth weight infants with and without treatment with Omegaven® (high n-3 fish oil supplement) and to establish whether omega-3 fatty acid supplementation in extremely low birth weight infants will reduce the incidence and severity of retinopathy of prematurity (ROP). The study intervention “drug product” has been used in the neonatal population via the same route of administration safely for other disease indications internationally and nationally including here at University of California San Diego. This investigation does not significantly increase the risk or decrease the acceptability of risk of our study population.

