Once enteral nutrition reaches desired minimum mL/kg/day (determined by the NICU neonatology team), then parenteral supplementation will be discontinued and enteral supplementation will begin. Carlson’s Fish oil ® (400 mg of omega 3 fatty acids: EPA 200 mg, DHA 125 mg, and 75 mg of other omega-3 fatty acids per ¼ tsp) will be given in the experimental group. Enteral fish oil supplementation of 1.25mL/kg/day (1/4 teaspoon per kg per day) divided at least every 12 hours for tolerance will be continued until the baby is at 40 weeks adjusted age or the retina is fully vascularized. We will adjust our fish oil dosage to maintain maximum enteral DHA supplementation to 125 mg/kg/day (omega3 400mg/kg/day). The total dose will be given BID initially. If there are any symptoms of GERD or other intolerance symptoms that are concerning to the primary team, then oral fish oil total daily dose will be divided over multiple administrations. If enteral oil is not tolerated even after medical management, we can decrease the amount by 25% until tolerated. We do not expect poor tolerance to this dose given 120 mg/kg/day has been tolerated as an emulsion via feeding tube without any complications²¹. As it is typical of this study population to require varying needs of care and drug administration, should any infant randomized to the Omegaven arm require discontinuation of the study drug for clinical reasons for more than

five days (either consecutive or accumulative), that infant will be withdrawn from the study. Drug administration disruptions occurring for 5 or less days (total) shall not be considered protocol deviations but will be recorded and noted in the annual FDA safety report.

Following discharge from the NICU and prior to infants reaching 40 wks, a research team member (other than the PI) will contact the parents with infants in the Omegaven arm once weekly to encourage parents to continue with the prescribe fish oil administration for their infant until he/she has is 40 weeks adjusted age.

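### T3, the last DHA and mRNA draw, has no upper age limit, so in infants still in hospital after 40 weeks it may be taken after fish oil has stopped

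*Combined protocol and SAP*

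**What the plan says.** All the timing rules are in section 9, Research Design and Methods.

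- **List of blood draws.** "Blood draw T3= Prior to discharge from hospital coinciding with time that ROP may be present", followed by a floor of 35 weeks adjusted age. The T1 and T2 entries each carry a grace period of plus or minus 3 days. T3 has none.
- **Lipidomics paragraph.** The same sample is described as "prior to discharge from hospital coinciding with time that ROP may be present", with no age floor.
- **Setting.** Blood is taken "at 4 different times spread apart while the infant is in the hospital", so no outpatient sample is planned.
- **End of supplementation.** The main text says "Fatty acid supplementation will continue until the baby is full term (40 adjusted weeks of age". The Nutrition text says enteral fish oil "will be continued until the baby is at 40 weeks adjusted age or the retina is fully vascularized".
- **Eye exams.** For both groups, "infants will have SOC eye examinations prior to discharge around 40 weeks GA", with a separate provision for infants discharged before 38 weeks. Serial exams usually run to 1 to 2 months post-term.
- **Statistical Analysis.** The primary outcome is DHA at 40 weeks. The analysis is a mixed model with group, time and their interaction, plus a random intercept and a random linear slope. It is said to deal with variable visit timing.

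**The concern.** T3 is the latest DHA value in the model and the sample closest to the 40-week primary time point. Its only upper bound is discharge, which is an event and not an age. In the experimental arm, whether the value reflects current supplementation can therefore depend on how long the infant stays, and length of stay plausibly tracks illness.

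If DHA declines once fish oil stops, off-treatment samples would pull the arm difference toward zero, add variance, and link measured DHA to how sick the infant was. The T3 mRNA comparison (Outcome 2) uses the same sample and has the same exposure.

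The missing 35-week floor in the Lipidomics paragraph is a separate matter. It permits earlier samples, not later ones.

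**Working it through.** **Step 1. Can a compliant T3 fall off treatment?** The T3 window opens at 35 weeks (list of draws) or at no stated age (Lipidomics) and closes at discharge. Fish oil stops at 40 weeks adjusted age. The phrase about the time ROP may be present does not cap the window at 40 weeks, because eye exams can run to 1 to 2 months post-term. An infant in hospital after 40 weeks and not yet sampled can therefore have a compliant T3 after fish oil has ended. If the alternative stop (full retinal vascularization) applies earlier, this can happen before 40 weeks too.

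**Step 2. Does the model absorb it?** A mixed model copes with unequal visit times. The one specified has a linear time trend and no term for supplementation status or time since the last dose. A straight line cannot represent a rise on treatment followed by a fall after stopping.

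**Step 3. Reproduce the plan's power.** Inputs from Power Calculations: mean pre-post changes of 42 and 27 µmol/L, so a difference of 42 − 27 = 15; largest SD considered 15; 40 infants, 20 per arm; two-sided alpha 0.05.

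- Noncentrality = difference / (SD × √(2/n)) = 15 / (15 × √(2/20)) = 3.16, with 38 degrees of freedom.
- Power = 86.9% by noncentral t (88.5% by normal approximation). This agrees with the plan's claim of over 80%.
- The difference detectable with 80% power at SD 15 is 13.6. Power therefore drops below 80% once the mean difference shrinks by more than 1 − 13.64/15 ≈ 9%.

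**Step 4. Dilution under assumed values.** Let f be the share of experimental-arm T3 samples taken off treatment and r the fraction of the arm difference remaining in those samples. The documents give neither, so both are assumptions.

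Diluted difference = 15 × [1 − f × (1 − r)]. For f = 0.2 and r = 0.5 this is 15 × 0.9 = 13.5.

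| f | r | Difference | Power, SD 15 | Power, SD 13 | Power, SD 11 |
|---|---|---|---|---|---|
| 0 | – | 15 | 86.9% | 94.5% | 98.8% |
| 0.1 | 0.75 | 14.625 | 85.2% | 93.4% | 98.4% |
| 0.2 | 0.5 | 13.5 | 79.2% | 89.2% | 96.6% |
| 0.2 | 0.25 | 12.75 | 74.5% | 85.6% | 94.6% |
| 0.3 | 0.5 | 12.75 | 74.5% | 85.6% | 94.6% |

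At SD 9, power is at least 99.2% in all four scenarios.

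The table holds the SD fixed. Mixing on- and off-treatment values also widens the experimental arm. For f = 0.2 and r = 0.5 its variance is 15² + 0.2 × 0.8 × (15 × 0.5)² = 225 + 9 = 234. The pooled SD is then √((225 + 234)/2) = 15.15, and power is 78.4% instead of 79.2%.

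As an extreme, suppose none of the difference remains (r = 0). Power at SD 15 is then 79.2%, 69.3% and 57.8% for f = 0.1, 0.2 and 0.3. At SD 9 it is still 94.9% for f = 0.3.

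These are single-time-point t-test figures, as in the plan. They ignore T1 and T2.

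**The case against.** The strongest reply is that the harm is possible but not shown. T3 may be taken at any time from 35 weeks, and nothing tells staff to wait for the day of discharge. A long-stay infant has about five weeks (40 − 35) in which a sample would be on treatment. The Eye exams text concerns examinations and does not forecast length of stay. If it is read as a forecast, it suggests discharge by about 40 weeks, and so few late samples. This stands: nothing in the documents supports an off-treatment share of 20% or 30%.

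It is also fair that SD 15 is the largest of the six values the plan considered, and that below it every scenario in the table keeps power above 80%. A reader might infer from the SD 15 column that the trial is underpowered because of T3. The documents do not support that.

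A reader might likewise infer that the absent floor in the Lipidomics paragraph causes off-treatment samples. It cannot. That paragraph may simply be a shorter restatement of the list.

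The plan can also point to its mixed model as the answer to variable timing. That holds for unequal visit times. It does not hold for a change in exposure before the sample, which the linear trend leaves unmodelled.

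**Conclusion.** The point holds as a gap in a stated sampling rule. T3 has no upper age, treatment has an end, and the analysis has no term for samples taken after that end. This rests on the text alone.

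The consequence for power rests on three assumptions: that some experimental-arm infants are sampled after fish oil stops, that DHA then falls, and that the SD is near the top of the plan's range. In the four scenarios, power at SD 15 runs from 85.2% down to 74.5%, against 86.9% with no dilution. It does not fall below 85.6% at SD 13 or 94.6% at SD 11. The true size cannot be determined from the documents.

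Two wording conflicts accompany the point: the 35-week floor that appears in only one of the two T3 descriptions, and the two wordings of when supplementation ends. Both need reconciling. This review takes no position on which stop rule is right. The change is a cheap improvement and does not mean the design fails.

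**What to change.** 1. Use one T3 definition in both the list of draws and the Lipidomics paragraph: taken with a routine blood draw from 35 weeks adjusted age, before discharge, no later than the end of supplementation, and as near to the 40-week primary time point as possible. Apply the same age limit in both arms, since controls have no supplementation end date of their own.
2. Reconcile the two wordings of when supplementation ends, so that the upper limit of T3 has one meaning.
3. Record postmenstrual age and supplementation status at T3, and use actual age as the time variable in the mixed model.
4. Keep any late samples in the main analysis and examine their influence in a sensitivity analysis. Dropping them would exclude infants because of a long stay, which is a post-randomisation event related to illness.

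The cost is protocol wording, a scheduling rule and two recorded items, with no extra blood sample. The downside is that a few long-stay infants are sampled earlier than they otherwise would be. A window from 35 weeks still does not guarantee a sample at exactly 40 weeks, so the age recorded at T3 is needed to interpret the primary value.
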